## Protocol Title

Comparative study of non-invasive Adhear bone conduction system to traditional bone conduction hearing devices

## Objectives\*

Aim 1. Determine if non-invasive Adhear is an equally effective treatment solution for unilateral profound sensorineural hearing loss when compared to invasive boneanchored implants.

Hypothesis: We hypothesize that non-invasive Adhear bone conduction technology will provide similar benefit to the more invasive bone anchored implant system for unilateral profound sensorineural hearing loss.

Aim 2. Non-invasive Adhear is an equally effective treatment solution for conductivehearing loss when compared to invasive bone anchored implants.

Hypothesis: We hypothesize that non-invasive Adhear bone conduction technology will provide similar benefit to the more invasive bone anchored implant system for conductive hearing loss.

Aim 3. Non-invasive Adhear is a more effective treatment solution for pediatric hearing loss when compared to bone conduction devices worn on a headband.

Hypothesis: We hypothesize that non-invasive Adhear bone conduction technology will increase objective and subjective benefit when compared to traditional bone anchored implant processors worn on a headband for pediatric conductive hearingloss.

Aim 3a. - To evaluate the validity of the non-invasive ADHEAR bone conduction hearing system in children with bilateral or unilateral conductive hearing loss

Aim 3b. To compare the benefits of the non-invasive ADHEAR bone conduction hearing system in children with bilateral and unilateral conductive hearing loss to traditional non- invasive bone conduction hearing systems worn on a headband.

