#### **Procedures Involved\***

The medical records of patients who received a bone conduction hearing device follow-up between January 1, 2010 through September 23, 2021 will be retrospectively reviewed. We anticipate review of approximately 500 medical records. Demographic data for review include gender, age, primary spoken language, and etiology. Standard clinical hearing outcome data will be reviewed for both groups and will include audiometric thresholds, word recognition ability, and speech perception measures. This information will be used to determine study candidates. Those who meet the inclusion criterion will be contacted for study participation. Once we have received a minimum of 10 but no greater than 30 participants for each study group, retrospective review will be completed and no new charts will be accessed. Participants will then only be studied prospectively. Demographic and audiometric data will be maintained under a unique identifier code linked to the consented study

participant for reference to study outcome data.

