### **Study Design**

#### **Aims 1&2**

- Experienced adult bone anchored implant recipients with either unilateral profound sensorineural hearing loss or conductive hearing loss will be enrolled for study. Subjects will be given the Adhear hearing system on trial for 2 weeks  $\pm$  90 days. Prior to dispensing of the experimental system, function of the subject's implant system will be verified. Custom pre-post subjective measures will be administered. Subjects will undergo behavioral measures of benefit in the 1) implant aided condition and 2) the Adhear Aided condition
- Conditions will be randomized by subject and will consist of the following:
  - Speech perception in noise ability using the BKBSIN (Etymotic, Elk Grove, IL) adaptive tests for speech front, noise front (0°/0° azimuth), speech poorer ear, noise better ear (90°/270° azimuth), speech better ear, noise poorer ear (90°/270° azimuth)
  - Soundfield aided narrow band signal thresholds – better ear plugged
  - Soundfield aided speech reception thresholds – better ear plugged
- At 2 weeks  $\pm$  90 days, subjects will undergo behavioral measures of benefit in the Adhear aided condition. Tests will be repeated using the subjects own processor on a soft headband to evaluate transcutaneous stimulation.
- Conditions will be randomized by subject and will consist of the following:
  - Speech perception in noise ability using the BKBSIN (Etymotic, Elk Grove, IL) adaptive tests for speech front, noise front (0°/0° azimuth), speech poorer ear, noise better ear (90°/270° azimuth), speech better ear, noise poorer ear (90°/270° azimuth)
  - Soundfield aided narrow band signal thresholds – better ear plugged
  - Soundfield aided speech reception thresholds – better ear plugged

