## **Data Management\***

Data collected includes: Gender, age, language, etiology and type of hearing loss, treatment ear, audiometric data including thresholds and speech outcomes, prior hearing treatment, date of activation or device use, aided thresholds, aided speech in noise performance, hours of device use, and subjective outcomes (see questionnaires included).

All the previously described data will be stored on the PI's computer and used for analyses purposes in room 526 of the clinical research building at the University of Miami Medical Center located at [name]. It will be password protected, and unique identifiers will be used for subject protection. Descriptive statistics will be used to report demographic (e.g. age and

gender) data. Quantitative data will be presented as mean, standard deviation (SD) and range (minimum and maximum); qualitative data will be presented as frequencies and percentages. Inferential statistics will be applied to detect differences in speech in noise performance as a function of transcranial attenuation. For this purpose, parametric Student's t-tests or nonparametric Wilcoxon signed rank tests will be performed, depending on the data distribution. Statistical significance will be set to  $p < 0.05$ . The subjective questionnaires will be summarized by visit using descriptive summaries. For numeric measures the change from baseline will be calculated and inferential tests applied. For categorical measures, a shift from baseline will be presented demonstrating the subjects as being better, the same, or worse.

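### Aims 1 and 2 claim that Adhear matches the implant, but the analysis plan only tests for differences and gives no Adhear-minus-implant contrast, margin or confidence-interval rule

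*Combined protocol and SAP*

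**What the plan says.** **Aims.** Under Objectives, Aim 1 is to "Determine if non-invasive Adhear is an equally effective treatment solution for unilateral profound sensorineural hearing loss" relative to the implant. Aim 2 reads: "Non-invasive Adhear is an equally effective treatment solution for conductivehearing loss when compared to invasive bone anchored implants". Both hypotheses expect similar benefit, and neither says how close the devices must be.

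**Measurements.** Study Design, Aims 1&2, is within-subject: "Subjects will undergo behavioral measures of benefit in the 1) implant aided condition and 2) the Adhear Aided condition". Condition order is randomised by subject, and speech in noise is measured with the BKB-SIN in three speech/noise configurations. After the trial period Adhear is tested again, and "Tests will be repeated using the subjects own processor on a soft headband to evaluate transcutaneous stimulation". The implant condition is listed only at the first session.

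**Analysis.** The analysis text is in Data Management: "Inferential statistics will be applied to detect differences in speech in noise performance as a function of transcranial attenuation". The method is that "parametric Student's t-tests or nonparametric Wilcoxon signed rank tests will be performed, depending on the data distribution", with significance at p < 0.05 and sidedness not stated. Questionnaires get descriptive summaries and a better/same/worse shift. In addition, "For numeric measures the change from baseline will be calculated and inferential tests applied".

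**Size.** Procedures Involved stops chart review "Once we have received a minimum of 10 but no greater than 30 participants for each study group". Study Populations sets a minimum of 10 for each adult group. Local Number of Subjects is 60. The documents give no margin, confidence-interval rule, SD, effect size or power.

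**The concern.** A test for differences has two possible results. If significant, it says the devices differ. If not, it says only that the data did not separate them. Neither is evidence that the devices perform alike, so the plan as written gives no valid route to the conclusion that Aims 1 and 2 seek. It also does not say what will be concluded when p ≥ 0.05, which leaves room to read that result as similarity.

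The contrast is open as well. Data Management frames the test by transcranial attenuation, not by device. With three configurations and two Adhear visits against one implant visit, each group has 3 × 2 = 6 possible Adhear-versus-implant speech-in-noise contrasts, and the choice could be made after the data are seen.

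The comparator is a surgically implanted device, and Potential Benefits to Subjects says the results will inform clinicians about non-invasive alternatives. An unsupported claim of equal effectiveness would feed directly into that use.

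**Working it through.** The plan has no power or sample-size figure to reproduce. The check asks what a non-significant result would mean at the planned sizes, and what margin those sizes could support.

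**Inputs**
- From the documents: n = 10 (minimum, Study Populations) and n = 30 (upper figure, Procedures Involved); significance level 0.05 (Data Management); paired measurements (Study Design, Aims 1&2).
- Derived: n = 15. The paediatric minimums are 10 + 15 + 10 = 35. Then 60 − 35 = 25 places remain for both adult groups, and 25 − 10 = 15 is the most one group can have while the other keeps its minimum. This assumes that groups do not overlap and guardians are not counted.
- Assumed: two-sided test; normal paired differences; effects in units of the SD of the paired difference.

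**Step 1: how often a real deficit is missed.** For a true deficit of d SD, the paired t statistic is noncentral t with n − 1 degrees of freedom and noncentrality d√n. Power is P(|T| > t(0.975, n−1)), and the chance of missing the deficit is 1 − power. For example, at n = 10 and d = 0.5 the noncentrality is 0.5 × √10 = 1.58 and the critical value is 2.262. Power is 0.293, so the deficit is missed 71% of the time.

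| n | Power, d = 0.5 | Missed | Power, d = 0.8 | Missed | d at 50% power |
|---|---|---|---|---|---|
| 10 | 0.293 | 71% | 0.616 | 38% | 0.69 |
| 15 | 0.438 | 56% | 0.821 | 18% | 0.54 |
| 30 | 0.754 | 25% | 0.989 | 1% | 0.37 |

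The last column limits the point: a deficit is missed more often than not only if it is smaller than that value.

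**Step 2: sensitivity at d = 0.5.** With a one-sided 0.05 test, power is 0.427, 0.578 and 0.848, so the deficit is missed 57%, 42% and 15% of the time at n = 10, 15 and 30. With the Wilcoxon signed rank test (two-sided, normal data, 20,000 simulations), it is missed about 72% at n = 10 and 26% at n = 30.

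**Step 3: precision.** The 95% CI half-width is t(0.975, n−1)/√n sample SDs: 2.262/√10 = 0.72, 2.145/√15 = 0.55 and 2.045/√30 = 0.37.

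**Step 4: margin supportable with 80% power when the true difference is 0.** Non-inferiority (one-sided 0.025) solves P(T > t(0.975, n−1)) = 0.80 with noncentrality margin × √n. Equivalence requires the whole interval to lie within ± the margin.

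| n | Non-inferiority, 95% CI | Equivalence, 95% CI | Equivalence, 90% CI |
|---|---|---|---|
| 10 | 1.00 SD | 1.15 SD | 1.00 SD |
| 15 | 0.78 SD | 0.90 SD | 0.80 SD |
| 30 | 0.53 SD | 0.61 SD | 0.55 SD |

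**Step 5: subjects needed for a 0.5 SD margin at 80% power.** Non-inferiority needs 34 per group. Equivalence needs 44 by the 95% CI, or 36 by the 90% CI. All exceed 30.

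**The case against.** Several points on the other side are fair.

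- **The comparison is not absent.** The aims name the comparator, Background says Adhear outcomes will be compared with those of traditional implants, each adult is tested with both devices, and a signed rank test is naturally paired. This stands as far as it goes: the intent is clear. But Data Management never carries it into an analysis, and on the most generous reading the test is still one for differences without a margin.
- **Other analyses are listed.** Descriptive summaries, questionnaire change and the better/same/worse shift are planned. None sets a criterion for similarity.
- **The soft-headband test has its own stated purpose.** It need not replace the implant comparator. Even so, no implant score is listed at the second session to pair with the later Adhear score.
- **No misreading is stated.** The plan does not say p ≥ 0.05 will count as similarity. The defect is a missing decision rule, but without one the aims cannot be answered.
- **The limit of 30 is soft.** It appears where chart review ends, and adults who present to the clinic may also enrol. However, under the assumptions used for n = 15, the total of 60 is tighter than 30. Counting the 10 guardians leaves 60 − 45 = 15 places, fewer than the 20 that the two adult minimums need.
- **The 95% CI equivalence rule is stricter than the usual 90% CI.** True, so both are shown. The conclusion is the same under either.
- **SD units have no clinical meaning here.** True: 0.5 SD could be trivial or important in dB, and the documents do not allow a conversion. At n = 30 the chance of missing a large deficit is small.

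**Conclusion.** The concern holds, and the plan must be changed before it can answer Aims 1 and 2. The core does not depend on any calculation: the aims claim similarity, the tests look for differences, and no rule connects the two.

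The calculations show why a non-significant result cannot fill the gap. At the minimum group size it is the likelier result for any true deficit below about 0.69 SD. At 30 subjects that threshold falls to 0.37 SD, so the risk is smaller but remains. These figures rest on a two-sided paired t-test, normal differences and SD units. A one-sided or Wilcoxon test changes the percentages but not the conclusion. The clinical size of the problem in dB is unknown, because the documents give neither an SD nor a clinically relevant difference.

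**What to change.** In Objectives and Data Management:

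1. Name the paired Adhear-minus-implant BKB-SIN difference (dB) as the analysis for Aims 1 and 2, separately in each adult group, and state which direction is a deficit.
2. Fix one speech/noise configuration and one Adhear visit as primary, with the rest secondary. The first-session pair is the only Adhear-versus-implant comparison made in one session with randomised order. The end-of-trial Adhear score follows wear but must be paired with an implant score from the earlier session. The plan should choose one and say why.
3. Report the mean paired difference with its 95% CI, and state that similarity will not be concluded from p ≥ 0.05.
4. By default, restate both aims as estimation of that difference.
5. If a similarity claim is kept, pre-specify a justified dB margin. Conclude non-inferiority only if the 95% CI excludes a deficit as large as the margin, or equivalence only if the whole 95% CI lies within ± the margin. Otherwise report the result as inconclusive. A 90% CI for equivalence is a less strict alternative, and the choice should be made in advance.

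**Cost.** Items 1 to 4 change wording only, with no extra patients or visits. Item 5 needs an agreed margin and a matching sample size, and a tight margin may not be feasible within the planned numbers. The downside is that with small groups the honest conclusion may be that the data are inconclusive.

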## Background\*

Implantable bone conduction technology has been well established as an efficacious and effective treatment solution. Despite this, adoption and acceptance rates for implantable bone conduction devices are low (Andersen et al, 2006; Desmet et al, 2012; Farber et al, 2012; Kompis et al 2001; Siau et al 2015). This has been attributed to aesthetics (Farber et al, 2012); and the need for surgery (Farber et al, 2012; Desmet et al, 2012; Siau, 2015). In fact Siau and colleagues suggestedthat rejection of implantable bone conduction technology is as high as 70% with nearly 30% attributed to subject opposition to surgery (Farber et al, 2012; Siau et al, 2015). In lieu of implantation, bone conduction devices can be anchored to a headband. Non-invasive bone conduction hearing technology is a promising alternative to implantable bone anchored systems. Significant gains in speech perception in quiet and in noise can be achieved with both implantableand headband bone conduction devices. These basic auditory functions are an essential component for effective communication and daily acts of living. Likewise, the inability to performsuch functions results in considerable reduction of quality of life, social exclusion, vocational limitations, and a high disability and handicap index. Issues related to comfort and increased visibility of headband devices, however, have limited the acceptance and use of

such systems. The Adhear (MEDEL, Corp) bone conduction hearing system is a novel hearing device providing non-invasive direct stimulation of the hearing organ via bone conduction without the need for a headband. In the Adjoin system (MEDEL, Corp) the audio processor attaches to a long wear adhesive adapter. The adhesive adapter is worn discreetly behind the ear and allows the processor to stimulate the temporal bone without the use of a visible headband or implant. This provides optimal placement of the processor for maximal stimulation of the hearing organ, as well as a more natural placement of the microphone for sound collection. This novel approach overcomes the key limitations of current treatment solutions and has the potential to impact individuals with mixed, conductive or unilateral hearing loss in substantial ways.

The ability to provide nonsurgical acoustic stimulation by bone conduction without the discomfort and stigma associated with using a headband will allow for increased adoption and acceptance, while providing the effectiveness of an implantable device. Further, such technology will increase access for both adult and pediatric bone anchored implant candidates. Utilizing Adhear technology provides a less invasive alternative for patients who are unable or unwilling to undergo bone anchored implant surgery and offers an innovative approach to resolving the auditory deficits associated conductive, mixed or unilateral profound hearing loss. In short, the outcomes of the proposed study will provide direct benefit to patients and improve clinical application.

The safety and effectiveness of bone anchored implants (BAI) for the treatment of conductive, mixed, and unilateral profound sensorineural hearing loss (UPSNHL) has been well established. The notable benefits associated with implantable hearing technology have increased the support for more invasive forms of treatment. However, a significant number of patients exist who are unable or unwilling to pursue an implantable solution for their hearing loss. Further, in the UPSNHL population, evidence suggests that patients can achieve equal benefits with non-invasive solutions (Snapp et al, 2016). For conductive and mixed hearing loss, BAIs have been demonstrated to have improved gain and sound quality over traditional hearing aids (Mylanus et al, 1995, Mylanus et al, 1998; Hol et al, 2005; McDermott et al, 2002;) and have been an optimal solution for those who have physiological limitations to using traditional hearing aids.

Until now, those who were unwilling or unable to undergo bone anchored implantation were limited to bone conduction devices on a headband, a solution that has been plagued with poor acceptance due to unfavorable aesthetics and discomfort with long-term use. In this study, subjective and objective hearing outcomes utilizing a novel hearing device branded as the Adhear providing non-invasive bone conduction stimulation (MEDEL, Corp) will be compared with outcomes using traditional BAI technology.

## **Inclusion and Exclusion Criteria\***

All subjects will be prospectively enrolled for study.

Aims 1 and 2 will include adult English speaking patients who are experienced users of BAIs for the

indication of either single sided deafness or conductive hearing loss. Experienced will be defined as greater than 6 months of device use and no intermittent function of the device within 2 weeks of enrollment. Aims 1 and 2 will require retrospective chart review to identify potential study subjects for recruitment. Subjects who spontaneously present to the clinic may also be enrolled should the meet inclusion criteria. Subjects will be limited to those who have normal hearing by bone conduction defined as a pure tone average of 25 dBHL or better at 500, 1000, 2000, & 3000 Hz in at least one ear.

Aim 3 will include English speaking children 5 to 17 years of age and their primary guardian who present to the clinic for treatment by BAI on a headband device for the indications of single sided deafness or conductive hearing loss. Because subjects for aim 3 have not previously been users of a BAIs, subjects for aim 3 will be recruited during spontaneous presentation to the clinic. Subjects will also be recruited for aim 3 from various sites using flyers and email. Subjects will be limited to those who have no prior use of a BAI or bone conduction hearing device, normal hearing by bone conduction defined as a pure tone average of 25 dBHL or better at 500, 1000, 2000, & 3000 Hz in at least one ear. For those children where this cannot be definitively established, children will be included who display clinical signs of normal bone conduction hearing beyond a reasonable doubt and may include such evidence as (but not limited to): auditory brainstem response, speech awareness thresholds, visual reinforcement audiometry, conditioning play audiometry, CT scans, etc.)

Aims 3 a & b are an extension of Aim 3 and will include pediatric bilateral or unilateral conductive hearing loss patients who are between the ages of 2 and 17 years of age and are currently managed by the UMEI with a bone conduction device attached to a softband will be enrolled for study.

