#### **Exclusion Criteria:**

The study is limited to English speakers, as speech perception measures are only available in English so non-native English speakers do not undergo the standard clinical protocol.

For aim 3, parents of English speaking subjects who do not speak English will not be specifically excluded. Due to the high incidence of English speaking children in Spanish speaking homes, for primary guardians who speak Spanish, Spanish materials will be provided. Children who have previous experience with a BAI or bone conduction hearing device will not be included for study.

Subjects will be screened for any allergies related to adhesives as the experimental device requires use of an adhesive adapter. Those reporting allergies to adhesives or highly reactive skin will be excluded from study as a precautionary measure.

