#### **Aim 3**

- Pediatric conductive hearing loss patients who are between the ages of 5 and 15 years of age and present to the UMEI hearing rehabilitation by bone conduction technology along with their primary guardian will be enrolled for study. Subjects will be evaluated in two phases:
  - Phase 1 – random assignment to trial with either a traditional bone conduction

device on a headband or an Adhear hearing system for 3 weeks  $\pm$  90 days. Pediatric and parent subjective questionnaires will be administered prior to and at the end of phase 1.

- Phase 2- trial with system alternate to that which was assigned for phase 1. Pediatric and parent subjective questionnaires will be administered prior to and at the end of phase 2.

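### Aim 3 eligibility admits single-sided deafness and ages 5 to 17, but its hypothesis and design cover conductive loss only and the design says ages 5 to 15

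*Combined protocol and SAP*

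**What the plan says.** The protocol defines the Aim 3 population in several places, and they do not agree.

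- **Inclusion and Exclusion Criteria.** Aim 3 takes "English speaking children 5 to 17 years of age and their primary guardian" who come for a headband device "for the indications of single sided deafness or conductive hearing loss". The bone-conduction criterion needs to be met in one ear only, so it does not screen out single-sided deafness.
- **Objectives, Aim 3 hypothesis.** The comparison is with "bone anchored implant processors worn on a headband for pediatric conductive hearingloss".
- **Objectives, Aim 3 lead sentence.** This is broader and names no type of loss: "Non-invasive Adhear is a more effective treatment solution for pediatric hearing loss when compared to bone conduction devices worn on a headband".
- **Study Design, Aim 3.** Those enrolled are "Pediatric conductive hearing loss patients who are between the ages of 5 and 15 years of age". They are randomly assigned to one system and then try the other. No stratification is described.
- **Study Populations and Consent Process.** At least 10 new pediatric candidates, type of loss not named, and at most 15 subjects for Aim 3.
- **Data Management.** Type of hearing loss is among the data collected. Inference is by t-test or Wilcoxon signed rank test at 0.05, with no mention of analysis by type of loss.

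The Exclusion Criteria remove neither children with single-sided deafness nor those aged 16 and 17.

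**The concern.** Staff screening by the eligibility section would accept a child with single-sided deafness, or a 16-year-old. Staff working from the design section would not. Both are current text.

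The type of loss matters more than the age limit. In adults the sponsor keeps the two indications apart: Aim 1 is unilateral profound sensorineural loss and Aim 2 is conductive loss, each with its own hypothesis and its own minimum of 10. In children the eligibility text allows both into one comparison, and nothing in the analysis text separates them again.

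Aim 3 also carries the protocol's only hypothesis that Adhear gives more benefit than its comparator; Aims 1 and 2 hypothesise similar benefit. With 10 to 15 children, two or three from outside the hypothesised population are a large share. A pooled estimate would average over an unplanned mix of indications and would not answer the question about conductive loss.

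**Working it through.** **Step 1. Compare the texts.**

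| Place | Type of loss | Age |
|---|---|---|
| Objectives, Aim 3 lead sentence | not specified | not given |
| Objectives, Aim 3 hypothesis | conductive | not given |
| Inclusion and Exclusion Criteria | single-sided deafness or conductive | 5 to 17 |
| Study Design, Aim 3 | conductive | 5 to 15 |
| Study Populations | not specified | not given |

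Two mismatches remain: type of loss (eligibility against hypothesis and design) and upper age (17 against 15). No other section resolves either.

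**Step 2. Look for a safeguard.** Randomization is not described as stratified, and no analysis by type of loss is planned. The type of loss is recorded, so a separation is possible but not specified.

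**Step 3. Illustrate the size.** The documents give no effect size, standard deviation, power or mix for Aim 3, so there is no plan figure to reproduce. The inputs are:

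- From the documents: n = 10 (minimum), n = 15 (maximum), significance level 0.05.
- Assumed: a two-sided paired t-test; within-child device differences that are normal with SD 1; mean 1.0 in conductive loss; mean e in single-sided deafness; k children with single-sided deafness.

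The test rejects when |mean difference / (s/√n)| exceeds the 97.5% point of t with n − 1 degrees of freedom. The expected pooled mean is [(n − k) × 1.0 + k × e] / n. For n = 10, k = 3 and e = 0 it is (7 × 1.0 + 3 × 0)/10 = 0.70. For e = 0.5 it is (7 + 1.5)/10 = 0.85. The pooled variance also grows when the two means differ, so power was obtained by simulation.

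| n | k | Pooled mean, e = 0 | Power, e = 0 | Pooled mean, e = 0.5 | Power, e = 0.5 |
|---|---|---|---|---|---|
| 10 | 0 | 1.00 | 80% | 1.00 | 80% |
| 10 | 2 | 0.80 | 55% | 0.90 | 70% |
| 10 | 3 | 0.70 | 42% | 0.85 | 65% |
| 10 | 5 | 0.50 | 22% | 0.75 | 54% |

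At n = 15 with e = 0, power falls from 95% with no such children to 39% with 7 and 30% with 8. If e = 1.0, the effects are equal and nothing is lost at either size.

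**Step 4. Price the restriction.** If the test uses only the children with conductive loss out of 10 enrolled, the same t-test with effect 1.0 has power 68% with 8 children, 60% with 7 and 40% with 5 (noncentral t). That beats the pooled test when e = 0 (55%, 42%, 22%) but not when e = 0.5 (70%, 65%, 54%). The reason to separate the groups is therefore that the test should match the hypothesis. A gain in power is not assured.

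**The case against.** The strongest reply is that the broader population may be the intended one. The Aim 3 lead sentence says pediatric hearing loss without a type, Study Populations names no type, and Potential Benefits to Subjects mentions both indications just before it turns to the Aim 3 children. On that reading the hypothesis and design are too narrow and the eligibility text is right. This stands: the documents do not show which text is the mistake, so the fix has to leave both routes open.

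A reader might infer several stronger points that the documents do not support.

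- **That a mixed trial could say nothing about conductive loss.** Type of loss is collected, so a conductive-only result can be extracted from fewer children. Aims 3a and 3b also compare Adhear with a headband or softband device in conductive loss alone.
- **That scores with the better ear plugged measure different things in the two groups.** No section says so. Aims 1 and 2 apply the same plugged-ear thresholds to both adult indications. In Aim 3 each child tries both systems, and plugging is not stated for the word test.
- **That the prior-use exclusion bars every child in Aims 3a and 3b.** The sentence "Children who have previous experience with a BAI or bone conduction hearing device will not be included for study" closes a paragraph that opens by limiting itself to Aim 3, and it repeats a limit set for Aim 3 in the inclusion text. Aims 3a and 3b have their own paragraph requiring current softband use. Because they are also called an extension of Aim 3, a clearer scope would help, but this is a wording matter.
- **That the steepest power losses are to be expected.** They assume no device difference at all in single-sided deafness, which nothing in the documents establishes.

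**Conclusion.** The contradiction is certain from the text: Aim 3 has two populations and two upper age limits in current sections. Following the eligibility section as written can produce a pooled comparison that does not test the Aim 3 hypothesis, and the analysis text does nothing to prevent it.

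The consequence is conditional. It depends on how many children with single-sided deafness enrol and on whether their device contrast differs, and the documents give neither. The illustrated loss at n = 10 runs from none to 58 percentage points (80% − 22%), the worst case being 5 such children with no effect. All of it rests on the assumed 1.0 SD effect in conductive loss. The mismatch between pooled result and hypothesis does not depend on those assumptions.

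The age discrepancy is secondary: it changes who may enrol but not the question asked. The plan should be corrected, and this can be done cheaply.

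**What to change.** 1. Bring the Objectives, the Inclusion and Exclusion Criteria and the Aim 3 Study Design to one Aim 3 population and one age range.
2. In Data Management, state that the Aim 3 hypothesis test uses children with conductive loss, and that any enrolled children with single-sided deafness are reported separately, using the type of loss already collected.
3. If the sponsor intends both indications, widen the Aim 3 hypothesis instead and report the device contrast by type of loss.
4. As a wording note, say in the Exclusion Criteria that the prior-use exclusion applies to the Aim 3 crossover and not to Aims 3a and 3b.

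No new data are needed. The cost is a few sentences, plus either a slightly narrower recruitment pool or fewer children in the Aim 3 test. For example, 7 of 10 remain if 3 have single-sided deafness.
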